## **SCIENTIFIC BACKGROUND**

Between 10-23% of people suffer of chronic pain in our country (1,2). In Spain, the duration and intensity of pain is higher than in the rest of European countries (2). The most important issue is the impact of chronic pain on life of the millions of people who suffer this condition and their relatives. Chronic pain is an important health problem, and it is frequently associated to great emotional distress, physical and social impairment, and reduction of quality of life. 29% of people with chronic pain come to have depression (2).

Pain is a bio-psychosocial phenomenon, and we must approach to chronic pain with this frame. The International Association for the Study of Pain defines pain as “a sensitive and emotional disturbing experience, which is associated to a real or potential tissue injury, or that it is describe as caused by this injury”. Chronic pain is a multidimensional phenomenon, which implies physical states and psychological variables. Pain has an affective and sensorial dimension, and it is frequently accompanied by the desire to stop, reduce or scape from its presence (4).

Chronic pain has not a protective function, as acute pain has. Chronic pain is a nosological entity itself, produces null functionality, and it is frequently physically, psychologically and socially destructive.

The holistic view of the phenomenon of pain implies a multidisciplinary intervention, in which physician, social workers, psychologist, physiotherapist... cooperate. Nonetheless, this kind of multidisciplinary intervention is not well implanted in our country yet.

The definition of chronic pain by the International Association for the Study of Pain meant a change regarding previous definitions, introducing two new concepts: first of all, it considers that pain is not just a nociceptive experience, but that it is also integrated by emotional and subjective components; and moreover, that pain may exist without somatic cause.

Memory, emotions, thoughts and expectations influence how the person perceives pain. Cerebral regions implied in emotion also participate in neural circuits that control directly the pathways of pain (5).

General experience is that pain comes to occupy a central place in life of the person who has it. Attention is permanently focused on the painful sensation. Attention processing is altered and is involved in the chronic pain syndromes pathogenesis.

The emotional state regulates pain, and also produces cognitive biases, and it is related to poor cognitive flexibility and experiential avoidance, which dominates the experience of the individual. Psychological flexibility is associated to lower pain intensity and lower interference of the pain in daily life, also to lower anxiety and depression and to better physical and mental functioning (6).

It has also been found a higher tendency to process pain situation as with lack of control, with tendency to rumination, consequences magnification and negative expectations. This processing style has been named "catastrophising". The use of passive coping strategies is associated to higher pain, worse functioning and negative mood (7). People who use active coping strategies to cope with pain have better functioning.

Another interesting psychological construct to the management of pain is "mindfulness". Mindfulness is defined as a "non-elaborative awareness, without judgement, focus on the present moment, with total acceptance of each thought, sensation or emotion that emerges in the attention field". Applied to the fear avoidance model, responding to pain with a "mindful" approach leads to a better mood and functioning.

Different groups of chronic pain patients share the same cognitive mechanisms of maladaptive coping with pain, as "catastrophising", and pain anticipation, as well as similar central mechanisms and neural networks of pain anticipation, which suggests that up-down processing is shared in different types of pain. This suggests the existence of common cerebral mechanisms and cognitive functioning in different types of chronic pain. Because of that, it is important to carry out studies that recruit patients according to their levels of maladaptive functioning, mental suffering and pain interference in daily life, and not according to the type or anatomy of pain or tissue injury.

Psychological treatments for chronic pain has been developing since the 60s: behavioural therapy, cognitive therapy, "third wave therapies" (Acceptance and Commitment Therapy and Mindfulness". It is common to find programs with multiples components: stimulation, graduate exercise, mindfulness, and coping strategies... (8). In general, clinical guidelines based on evidence for fibromyalgia recommend multicomponent treatments (8).

Cognitive-behavioural approaches to chronic pain have been the predominant psychological treatments in the last 30 years. These approaches focus on create a cognitive and behavioural change in order to help the person with chronic pain to suffer less, cope better and use less medical services for his/her pain. These programs look for reducing pain by modifying physical sensations, catastrophising thoughts and maladaptive behaviour (9).

Recent meta-analysis reveal that Cognitive-Behavioural Therapy (CBT) has a beneficial effect on the standard patient, in a wide range of outcomes measures. CBT for chronic pain is a therapy with evidence and empirical support. However, CBT benefits to chronic pain are not as big and

general as they could or should be, having only a small size effect on disability. Not all patients respond to CBT (9). Moreover, much of the benefits are not maintained in the long term (8). Because of that, other types of interventions are appearing in order to try to demonstrate their effectiveness and cover the limitations of CBT. Among these new interventions we can find “Third wave therapies”, as Acceptance and Commitment Therapy (ACT) and Mindfulness-based therapies. ACT focuses on promoting psychological flexibility. It implies conscious acceptance and no judgement of the experiences, personal values identification and appropriate action to the goals sustained by these values. Until the date, it exists randomized clinical trials that demonstrate the effectiveness of ACT for chronic pain (10). Although ACT, Mindfulness-Based Stress Reduction programs (MBSR) and Mindfulness-based Cognitive Therapy (MBCT) can be distinguished by their theoretical assumptions, they share common basic concepts as acceptance and mindfulness. Recent meta-analysis conclude that therapies based on acceptance and mindfulness for chronic pain produce low to moderate size effects similar to those achieved by CBT (11).

Mindfulness improves emotional regulation, decreases experience avoidance and fear, modulates pain perception and stimulates structural and functional cerebral changes toward a better adaptation to pain. Mindfulness-based interventions have demonstrated their effectiveness to manage chronic pain in many studies (12).

The construct “self-compassion” is currently acquiring attention in the investigation due to its strong link to psychological health (13). However, investigation on self-compassion is still taking its first steps; and most investigation has been carried out with no clinical population. “Self-compassion” concept means “be touched by the own suffering”(12). Self-compassion can be understood as a useful strategy for emotional regulation in which painful feelings are not avoided but taken into account with consciousness, kindness, understanding and a common humanity feeling.

Mindfulness in the context of self-compassion implies to be aware of the own pain experience in a balanced way. Clinical investigation indicates that people who are self-compassionate have better psychological health than people who are not (13). Being self-compassionate implies having the skills to cope with life stressors in an effective way, for example with chronic pain (13; 15). It has been demonstrated that self-compassion training promotes self-care capacity in people with VIH or Diabetes Mellitus (16,17).

Neff and Germer have developed a specific program to increase self-compassion called “Mindful Self-Compassion” (MSC), which can be applied to general population and to certain clinical population (13). In no clinical population, MSC has demonstrated significant benefits in self-compassion and depression.

In spite of the promising results of interventions based on acceptance and self-compassion, we have still little data that allow back them as an effective intervention to the psychological approach to chronic pain.

## **OBJECTIVES AND HYPOTHESIS**

The objective of this study is to analyse the effectiveness of the MSC program versus the CBT program in order to improve self-care, compassionate relation to oneself, quality of life in a chronic pain patient’s sample. Both treatments are conducted in groups, are psychotherapeutic oriented, both have an 8 weeks duration, weekly frequency, 2 and a half hours per session.

The principal hypothesis of this investigation is:

- MSC program will be, at least, as effective as the CBT program in order to improve self-care capacity and self-compassion in chronic pain patients (decreasing self-criticism, isolation feelings, and thoughts over-identification) at the post-treatment time and in a 6-months follow-up.

Secondary hypothesis:

- MSC program will be, at least, as effective as CBT program in order to improve quality of life, and acceptance capacity; and as effective as CBT to reduce catastrophizing, daily life interference, anxiety and depression in a chronic pain patients simple, at the post-treatment time and a 6 months follow-up.

- We also hypothesize that MSC program will be, at least, as effective as CBT program in order to maintain the achieved benefits in a 6 months follow-up.

- Treatment satisfaction will be higher in MSC program, being treatment adherence higher in this program than in CBT program.

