## **METHODS**

We wrote a investigation protocol which has already been approved by the Research Ethics Committee of Hospital Universitario La Paz, Madrid.

This is a prospective experimental study; blind randomized, with parallel groups and final blind analysis with, at least, 64 patients with chronic pain.

All patients will be assessed at the pre-intervention moment, at the post-intervention moment (8 weeks), and in a 6 months follow-up.

This is a pre-post experimental design with which we intend to compare the effectiveness of 2 psychotherapeutic treatments for chronic pain. The two arms of treatment of this Randomized Clinical Trial are:

a) Mindful Self-Compassion Program (MSC)

b) Cognitive-Behavioural Program for chronic pain (CBT).

Both treatments are conducted by experimented clinicians with wide experience in chronic pain. We will conduct 8 therapeutic groups in total (4 for each arm treatment), with approximately 15 people per group.

We have estimated that we need a N=64 in order to detect significant differences in the principal outcome (self-care and self-compassion) with a size effect=0.5, SD=0.6, alpha=0.05 and power=90%.

During the investigation we will create a Data Base in accordance with current regulations. Data will be use following the principles contained in the Organic Law 15/1999, 13th December, of Personal Data Protection. All data will be electronically introduced in this database and data analysis will be conducted using SPSS 18.0.

It will be conducted an exploratory study of all variables previous to statistical analysis in order to identify anomalous data.

It has been done a first-step approximation to the behaviour and variability of the main outcome of the study with a 30 patients simple randomized to both arms in order to estimate the necessary N of the study.

Descriptive analysis of qualitative variables will be expressed in terms of frequencies and percentage, and analysis of quantitative variables will be expressed in terms of mean, standard deviation, median and interquartile range. The analysis will be conducted by intention to treat. Comparison of qualitative variables between groups of interventions or between segmentation factors will be conducted with Fisher test. We will apply t-Student, Mann-Whitney, ANOVA or Kruskal-Wallis test in quantitative variables, depending on the normality of the variable (tested with Kolmogorov-Smirnov-Lilliefords test) and the number of compared categories..

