Analysis of the changes along the treatment on principal and secondary outcomes of effectiveness will be conducted through a General Lineal Model (ANOVA with repeated measures), which allows checking if there are statistical significant differences in these changes based on arm of intervention.

Regression models will be conducted in order to identify prognostic factors.

Variables "Treatment satisfaction" and "adherence to treatment" will be compared using t-Student test for independent samples for patients who complete the treatment.

Aetiology of chronic pain will be taken into account when it is known.

Given the shortage of studies until the date referred to the effects of interventions based on self-compassion in chronic pain patients, the results of this study may give empirical date about the effectiveness and the need of mindful-self-compassion-based interventions, integrated in a multidisciplinary, approach to improve quality of life and self care in chronic pain patients.

Now, we go on to describe the two arms of treatment tested in this study:

- Mindfulness Self-Compassion (MSC) is a standardized program to increase self-compassion. It has been developed by Neff and Germer. The structure of the program is similar to de Mindfulness-Based Stress Reduction program (MBSR), with duration of sessions between 2 and 2 hours and a half. The frequency of the sessions is one per week for 8 weeks, with practical and experiential exercises in sessions and between sessions. The MSC program focuses primary on helping patients to develop self-compassion, and it includes Mindfulness just as a secondary component. The MSC program will be conducted by a clinician trained in this specific program.

- CBT: It has been adapted a Cognitive-Behavioural Intervention for Chronic Pain by Moix and Kovacs. Our program will have 8 sessions, with duration of sessions between 2 and 2 hours and a half. The frequency of the sessions is one per week for 8 weeks, with homework between sessions. During these 8 sessions we will train the following techniques: psycho-education about pain, relaxation training, cognitive restructuring training, solving problem training, psycho-education about emotions, interpersonal skills and time organization.

There we present the variables of the study:

Primary Outcome Measure:

- Self-Compassion: Self-Compassion Scale (SCS, long version). Self-compassion and Self-care. Self-kindness, Common Humanity and Mindfulness.

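### The principal hypothesis is a non-inferiority claim, but the trial is sized and analysed to detect a difference, with no margin or confidence-interval rule

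*Combined protocol and SAP*

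**What the plan says.** In the section on objectives and hypotheses, the principal hypothesis is that the "MSC program will be, at least, as effective as the CBT program in order to improve self-care capacity and self-compassion", at post-treatment and at 6 months. The secondary hypotheses take the same form. One reads "MSC program will be, at least, as effective as CBT program in order to improve quality of life, and acceptance capacity" and continues "as effective as CBT to reduce catastrophizing, daily life interference, anxiety and depression"; another applies the form to maintenance of benefit at 6 months. Only satisfaction and adherence are predicted to be higher with MSC.

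The Methods section works differently. The sample size statement says "we need a N=64 in order to detect significant differences in the principal outcome (self-care and self-compassion"), using an effect of 0.5, SD 0.6, alpha 0.05 and 90% power. Change over time is analysed by a repeated-measures ANOVA, "which allows checking if there are statistical significant differences in these changes based on arm of intervention". The other between-arm tests listed (Fisher, t, Mann-Whitney, ANOVA, Kruskal-Wallis) are also tests of difference. On numbers, 64 is a minimum; the plan also says "We will conduct 8 therapeutic groups in total (4 for each arm treatment), with approximately 15 people per group", which is about 8 × 15 = 120 patients. On the analysis set: "The analysis will be conducted by intention to treat".

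The plan gives no non-inferiority margin and no confidence-interval rule. Neither of the two follow-up times is made primary, and nothing says how a non-significant result will be read.

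**The concern.** A test of difference can support a claim of being no worse only when the new treatment wins significantly. If the two programmes perform alike, the likely result is p>0.05, and that does not show that MSC is no worse than CBT. The plan is silent on exactly this outcome. The risk is that absence of a significant difference is reported as confirming the principal hypothesis, so that a less effective programme is described as equivalent to an established therapy. The secondary outcomes worded in the same way carry the same gap. Without a margin, nobody can say whether 64 or about 120 patients is enough for the principal question.

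**Working it through.** **Inputs from the plan (Methods):** difference 0.5, SD 0.6, alpha 0.05, power 90%, minimum total 64, and 8 groups of about 15.

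**Assumptions:** equal allocation, so n = 32 or 60 per arm; 0.5 read as raw SCS points; a two-sample t-test at one time point; no dropout, therapy-group clustering or baseline adjustment. The deficits, advantages, margins and correlations below are illustrative, because the plan gives none.

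**Step 1: the plan's own figure.** With SE = SD·√(2/n), n = 32 gives 0.6·√(2/32) = 0.150. The noncentrality is 0.5/0.150 = 3.33. A two-sided 5% t-test on 62 df has power 90.7%, and 32 is the smallest n per arm that reaches 90%. So 64 is reproduced exactly as a two-sided superiority calculation. A one-sided 5% test would need only 52. At n = 60 the SE is 0.110 and the power is 99.5%.

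**Step 2: precision.** The 95% CI half-width is t(0.975, 2n−2)·SE: 1.999 × 0.150 = 0.30 at 32 per arm, and 1.980 × 0.1095 = 0.22 at 60.

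**Step 3: what the difference test delivers.** Noncentral t with noncentrality (true difference)/SE:

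| True MSC − CBT | Event | 32 per arm | 60 per arm |
|---|---|---|---|
| 0 | significant MSC win | 2.5% | 2.5% |
| +0.1 | significant MSC win | 10% | 15% |
| +0.2 | significant MSC win | 26% | 44% |
| −0.2 | non-significant | 74% | 56% |
| −0.3 | non-significant | 50% | 22% |

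**Step 4: the same check with the planned ANOVA.** This was simulated with three visits, compound symmetry, 0.6 taken as the SD of scores, and the deficit present at both later visits. The probability of a non-significant time × arm test for deficits of 0.2 / 0.3 is:

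| Within-patient correlation | 32 per arm | 60 per arm |
|---|---|---|
| 0.5 | 75% / 49% | 55% / 19% |
| 0.7 | 60% / 24% | 33% / 4% |

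Under true equality at 32 per arm, a significant test with MSC ahead at both later visits occurs in about 1.5–2% of trials.

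**Step 5: what a non-inferiority test would need.** Non-inferiority is shown if the lower limit of the two-sided 95% CI for MSC − CBT exceeds −margin. With true difference 0, the noncentrality is margin/SE:

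| Margin (points) | Power, 32 per arm | Power, 60 per arm | Total N for 90% |
|---|---|---|---|
| 0.2 | 26% | 44% | 382 |
| 0.3 | 50% | 78% | 172 |
| 0.5 | 91% | 99% | 64 |

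The smallest margin with 90% power is 0.49 at 32 per arm and 0.36 at 60. If both time points must pass at margin 0.3, and the two estimates correlate 0.5 to 0.7, power is 33–37% at 32 per arm and 65–68% at 60.

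**The case against.** The strongest reply is that this is a coherent superiority design with one loosely worded sentence. The stated objective is simply to compare the programmes, non-inferiority is never named, 64 reproduces exactly as a two-sided superiority size, and the analysis tests a difference. On that reading only the hypothesis needs rewording. But the wording recurs across the hypotheses, and the same section predicts a higher result only for satisfaction and adherence, so the two forms were distinguished. Even if superiority was meant, the text must change.

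These further points are fair in part:

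- The plan never says that p>0.05 will be taken as support. The false-reassurance figures are therefore conditional on that reading. The plan does not rule it out either.
- Both follow-up times are named in the hypothesis. What is missing is which one decides, or that both must.
- The t-test figures are not those of the planned ANOVA. At correlation 0.7 the ANOVA is clearly less permissive, as Step 4 shows, but it still supplies no margin.
- The required sizes assume no baseline adjustment. If 0.6 is the SD of scores (the plan does not say whether it is of scores or of change) and baseline is a covariate, the SD becomes 0.6·√(1−r²), which is 0.52 at r = 0.5 and 0.43 at r = 0.7. Margin 0.3 then needs about 130 or 88 patients for 90% power, not 172. Dropout and clustering would push the other way.

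**Conclusion.** The concern holds. The hypothesis and the test do not match, so a true hypothesis of equality could hardly ever be supported: 2.5% of trials with a t-test, and about 1.5–2% with the planned ANOVA at 32 per arm. Reading non-significance as support would pass an MSC programme 0.3 points worse in about 50% of trials at 32 per arm and 22% at 60 (t-test), or 24% and 4% with the ANOVA at correlation 0.7. The arithmetic behind 64 is sound for superiority, and a significant MSC win would support the hypothesis without any margin. Whether 64 is too few for non-inferiority cannot be judged: it suffices at a margin of 0.5, which is the whole difference the trial was sized to detect, and falls well short at 0.3 under the stated assumptions. The mismatch itself does not depend on any assumed figure.

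**What to change.** Choose one option before outcome data are examined by arm.

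**(a) Keep the non-inferiority claim.** Fix and justify an SCS margin. Name the primary time point, or require both. Make the claim only if the lower limit of the two-sided 95% CI for MSC minus CBT lies above minus the margin at the named time or times. Restate the power of the planned N (64 or about 120) for that rule. Define a per-protocol set and report that analysis beside intention to treat. For the secondary outcomes, either set margins too or make no non-inferiority claim.

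**(b) Restate the hypotheses as two-sided superiority,** which matches N=64, and state that p>0.05 will not be interpreted as equal effectiveness.

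Under either option, report between-arm 95% CIs at both time points for every outcome worded in the non-inferiority or equality form. For the maintenance hypothesis, add the between-arm contrast in change from post-treatment to 6 months. Because the main outcome was already explored in 30 randomised patients, state whether that was done by arm and whether those patients count in the trial; this bears on whether a margin set now is blind.

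**Cost.** Option (b) is a wording change and gives up the claim unless MSC wins significantly. Option (a) is also protocol and SAP text, but a tight margin means either accepting lower stated power or recruiting more: about 172 patients at 0.3 and 382 at 0.2 for 90% power, unadjusted. Neither option needs new measurements.

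### The separate hypothesis that MSC maintains benefits at 6 months no worse than CBT has no defined measure, contrast or margin, and the planned three-visit ANOVA cannot answer it

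*Combined protocol and SAP*

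**What the plan says.** Under Objectives and Hypothesis, the principal hypothesis and the first secondary one already compare the arms on improvement "at the post-treatment time and in a 6-months follow-up" (the secondary one in near-identical words). A further secondary hypothesis is then added: MSC will be "at least, as effective as CBT program in order to maintain the achieved benefits in a 6 months follow-up". Nothing says whether maintenance means absolute loss after treatment, the share of the gain retained, or change from baseline to 6 months.

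Under Methods, patients are assessed "at the pre-intervention moment, at the post-intervention moment (8 weeks), and in a 6 months follow-up". One analysis covers change, introduced as "Analysis of the changes along the treatment on principal and secondary outcomes of effectiveness". The method named is a repeated-measures ANOVA, and its stated purpose is "checking if there are statistical significant differences in these changes based on arm of intervention". No contrast between 8 weeks and 6 months is named, and no margin is given for any of the hypotheses that MSC is no worse than CBT. Analysis is by intention to treat. No method for missing scores is stated.

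**The concern.** Because 6-month improvement is covered by other hypotheses, the maintenance hypothesis adds something only if it concerns what happens between 8 weeks and 6 months. The planned test does not isolate that period. It responds to any difference in the pattern of the three means, including one that arises entirely during treatment, and it looks for a difference when the claim is that MSC is no worse.

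The analyst would then have to choose a measure of maintenance, possibly after seeing the data. The obvious choice, change from 8 weeks to 6 months, starts from a score that treatment has already moved. An arm that gained little has little to lose.

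Durability is not a side issue here. The Scientific Background gives the fading of CBT benefits as a reason for studying newer therapies.

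**Working it through.** **The plan's own figure.** Methods gives "size effect=0.5, SD=0.6, alpha=0.05 and power=90" per cent for N=64, the number needed "in order to detect significant differences in the principal outcome". Taking 0.5 as a raw difference, two-sided, 1:1:

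- Normal approximation: 2 × (1.960 + 1.282)² × (0.6/0.5)² = 30.3, so 31 per arm, 62 in total.
- t-based: 31.25, so 32 per arm, 64 in total.

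The figure reproduces, but it is sized for a difference and says nothing about maintenance. I take from it n = 32 per arm and SD = 0.6.

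**Assumed inputs (not in the documents).** Equal correlation ρ between visits of 0.5 to 0.8, SD 0.6 at every visit, complete data, and illustrative gains and retained shares.

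**1. The planned arm-by-time test when both arms keep everything.** Gains are 0.25 (MSC) and 0.50 (CBT), fully retained.

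- Arm differences at the three visits: 0, −0.25, −0.25. Their mean is −0.167.
- Sum of squared deviations: 0.167² + 2 × 0.083² = 0.0417.
- Non-centrality: (n/2) × 0.0417 / [SD² (1 − ρ)] = 16 × 0.0417 / [0.36 (1 − ρ)].
- ρ = 0.5 gives 3.70, ρ = 0.7 gives 6.17, ρ = 0.8 gives 9.26.
- Probability of p < 0.05 on F with 2 and 124 degrees of freedom: **38%, 59% and 77%**. Simulation of 10,000 trials per setting gave 38%, 58% and 77%.

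Maintenance is identical in the two arms. The test rejects only because the gains differ.

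**2. The unspecified alternative: change from 8 weeks to 6 months.** SE of the arm difference in change = 0.6 × √[2(1 − ρ)] × √(2/32), which is 0.150 at ρ = 0.5 and 0.095 at ρ = 0.8. Both arms retain half of their gain, so proportional maintenance is equal.

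| Gain, MSC v CBT | Mean loss, MSC v CBT | MSC shows the smaller loss | Significant in favour of MSC |
|---|---|---|---|
| 0.50 v 0.50 | 0.25 v 0.25 | about 50% | about 2.5% |
| 0.25 v 0.50 | 0.125 v 0.25 | 80% to 91% | 13% to 25% |
| 0 v 0.50 | 0 v 0.25 | 95% to 99.6% | 37% to 74% |

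The third column is Φ(difference in loss / SE), for example Φ(0.25/0.150) = 95%. The fourth is the upper tail of the non-central t test on 62 degrees of freedom. In the last row CBT patients are better off at 6 months by 0.25, yet the contrast nearly always points to MSC. If neither arm loses anything, the third column returns to 50%.

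**3. The same effect in the other direction.** Assume MSC gains 0.50 and keeps 0.35, CBT gains 0.10 and keeps 0.10, and ρ = 0.7. The change contrast is (0.35 − 0.50) − 0 = −0.15 for MSC. The 6-month difference is 0.35 − 0.10 = +0.25.

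| Per arm | Change contrast, SE and 95% CI | 6-month difference (unadjusted), SE and 95% CI |
|---|---|---|
| 60 (4 groups of about 15) | 0.085; −0.32 to 0.02 | 0.110; 0.04 to 0.46 |
| 32 (N=64) | 0.116; −0.38 to 0.08 | 0.150; −0.04 to 0.54 |

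The two estimates have opposite signs. At 60 per arm, MSC would fail a maintenance criterion at any margin below 0.32 while its 6-month interval lies above zero.

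**The case against.** The strongest reply is that the plan never says loss will be measured from the 8-week score. That is correct. A reader might infer that the trial has chosen an invalid, non-randomised comparison, and the documents do not support that. The arm difference in mean change from 8 weeks to 6 months equals the 6-month arm difference minus the 8-week arm difference. Under intention to treat with complete data both are randomised contrasts, so the result is a valid estimate with the right error rate for equal change. The difficulty is one of meaning, and it arises only when gains differ and loss grows with gain. Restricting to improvers, or adjusting for the 8-week score, would be a different matter, but neither is planned.

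A reader might also take the last illustration as two opposite conclusions from the same data. It is not. At 60 per arm the change interval includes zero, and at 32 per arm both intervals do.

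It can further be said that the 6-month hypotheses would show which arm ends better, and that a hypothesis about achieved benefits presupposes a gain. Both points limit the damage. Neither supplies a measure, a contrast or a margin, and neither stops the arm-by-time test from being read as the answer on maintenance.

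**Conclusion.** The concern holds in this form. A stated secondary hypothesis is undefined, and the one planned analysis of change cannot answer it. That analysis can be significant solely because gains differ (about 38% to 77% of trials under the assumptions shown), and a non-significant result would not establish that MSC is no worse. The obvious substitute contrast is statistically valid but is confounded with the size of the initial gain, so it can favour the arm that is worse off at 6 months. With equal gains, or with no loss in either arm, that distortion disappears.

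The percentages rest on assumed gains, retention and correlations, with 32 per arm and SD 0.6 taken from the plan. They show that the problem can be large and do not forecast this trial. Only a secondary hypothesis is affected, but it is a prominent one and cheap to repair.

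**What to change.** Replace the maintenance hypothesis and add a matching sentence to the analysis, for example: *Durability will be judged on the between-arm difference at 6 months, adjusted for the pre-treatment score, in all randomised patients. Its 95% confidence interval will be read against a non-inferiority margin fixed before unblinding. Change from 8 weeks to 6 months will be shown by arm, beside each arm's gain at 8 weeks, as description only and without a test of maintenance.*

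The sponsor has to choose and justify the margin, since the documents give none, and has to state how missing 6-month scores are handled so that all randomised patients can be included. No new data are needed.

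The cost is that durability is then answered by the same 6-month comparison as the other hypotheses and is no longer an independent claim.
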